All ARs developed during the study in female patients withdrawn from the study, including ARs to the moment of terminating participation of female patient in the study will be analyzed and included into a final report on the study performance.

If withdrawal/exclusion from the study was after administration of the study drug to a female patient, her data collected before the moment of withdrawal/exclusion from the study will be analyzed during analysis of safety and, if possible, during analysis of efficacy. Approaches to analysis of data on the study participants early terminated their participation in the study are described in section 9.5.

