5.3.3 Substitution procedure

Female patients withdrawn before randomization will be substituted by new female patients (in the volume considered by the calculated number of female patients screened). Female patients withdrawn from the study after randomization and beginning of the therapy will not be replaced by new ones, and their data will be considered in the final analysis (see section 9.5).

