9.5 Procedures for accounting absent, unevaluable and doubtful data

At monitoring visit in the clinical site, monitoring officers authorized by the Sponsor will perform analysis of CRFs of the study subjects to check for absence of the required data. In case of absence of data in CRF and presence of respective information in the primary documentation, questions to the Investigators and assignments for elimination of non-conformities will be sent.

When checking database of the study results, a statistician authorized by the Sponsor and the Principal Investigator will perform analysis with respect to doubtful, omitted and unevaluable data by results of which the questions to the Investigators will be sent.

When applicable, the Investigators will eliminate the revealed errors in the CRF and inform the Principal Investigator and authorized representatives of the Sponsor on it. If the errors found in data will be impossible to be corrected after completion of female patient participation in the study, during statistical analysis of data, an analysis of sensitivity of the resulting parameters to presence

of doubtful data will be performed. Information on omitted, doubtful and unevaluable analysis of data will be provided in the final report on the clinical study.

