9.7 Selection of the study subjects for the analysis

9.7.1 Intent-to-treat population (ITT)

ITT set, also known as full analysis set, comprises all the randomized patients administered the study drug regardless of the degree of compliance with the protocol during the study. This set of data is main for the analysis; it will be used for evaluation of all the planned parameters.

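### Do sections 5.3.3 and 9.7.1 disagree on whether women withdrawn during surgery, before dosing, enter the main analysis?

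*Protocol*

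**What the plan says.** Section 4.2.4.2 of the Protocol lists randomisation among the steps before surgery on Day 0, and 4.2.1 places the study drug at the final stage of the operation. Section 5.3 makes intraoperative conversion and the need for a drain withdrawal criteria, and 5.3.1 has the woman leave when the reason is found.

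Three sections bear on such women in the analysis:

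- **5.3.3** covers "Female patients withdrawn from the study after randomization and beginning of the therapy", who "will not be replaced by new ones, and their data will be considered in the final analysis (see section 9.5".
- **5.3.2** covers withdrawal after the drug was given. Data collected up to withdrawal "will be analyzed during analysis of safety and, if possible, during analysis of efficacy". It then adds: "Approaches to analysis of data on the study participants early terminated their participation in the study are described in section 9.5". It also provides for analysis of "All ARs developed during the study in female patients withdrawn from the study".
- **9.7.1** defines the ITT set, which "comprises all the randomized patients administered the study drug", and adds: "This set of data is main for the analysis; it will be used for evaluation of all the planned parameters".

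Section 9.5, to which 5.3.2 and 5.3.3 both point, deals with checks of the case report form, queries to investigators and, for errors that cannot be corrected, "an analysis of sensitivity of the resulting parameters to presence" of doubtful data. It says nothing on withdrawn women.

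On timing, 4.2.4.4 gives a woman withdrawn in hospital her withdrawal visit, MRI included, on the same day. The primary endpoint in 4.1 speaks of a repeated MRI without naming a day. Section 7.2 sets the efficacy evaluation at Visit 3, and 4.5 puts it at Day 30±4.

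**The concern.** Section 5.3.3 depends on when therapy begins, and the Protocol does not say. The heading of 4.2.4.2, Therapy period, opens with the visit that contains randomisation and surgery. If therapy starts there, 5.3.3 brings into the final analysis women whom 9.7.1 leaves out, and the section cited to settle the matter is silent.

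Their only repeat MRI would be a Day 0 scan, taken before the Day 3 to 14 collagen response described in 2.1. Adhesions have just been divided, so it might look like a response in either arm. On a loose reading, one analyst could omit these women, another count them as failures and a third count them as responders. Adding the same number of responders to both arms shrinks the difference between them. With 24 completers per arm, one or two women can matter in a close result. A similar question arises for dosed women withdrawn before discharge, who are in the 9.7.1 set but have no Visit 3 scan.

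**Working it through.** **Inputs.** Section 9.2 and the synopsis give 45% on Seroguard, a margin of 5 points, one-sided 5% and 80% power. The placebo rate is 10% in the synopsis and in the reasoning of 9.2; the symbol list in 9.2 prints 5%. Each arm has 26 randomised and 24 completed.

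**The plan's own figure.** With variance p1(1−p1) + p0(1−p0):

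n = (0.45×0.55 + 0.10×0.90) × ((1.645 + 0.842)/(0.45 − 0.10 − 0.05))² = 0.3375 × 68.7 = 23.18, so 24 per arm. The stated figure reproduces with the 10% placebo rate.

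**Size of the three treatments.** The Protocol gives no number of women withdrawn before dosing. The allowance is 26 − 24 = 2 per arm for all withdrawals after randomisation, so up to 2 per arm is shown. For u women added per arm, with a share r counted as response:

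p′ = (24p + r·u)/(24 + u)

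power = Φ[(p1′ − p0′ − 0.05)/√((p1′(1−p1′) + p0′(1−p0′))/(24+u)) − 1.645]

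| Treatment of undosed women | Rates | Power |
|---|---|---|
| Left out (9.7.1) | 45.0% v 10.0% | 81.2% |
| One per arm, failure | 43.2% v 9.6% | 79.9% |
| Two per arm, failures | 41.5% v 9.2% | 78.6% |
| One per arm, response | 47.2% v 13.6% | 76.3% |
| Two per arm, responses | 49.2% v 16.9% | 72.0% |

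Enumerating all 24 v 24 outcomes with a Wald test gives 81.4% left out, 78.6% with two failures and 75.1% with two responses. On this fuller count the extreme case costs about 6 points, not 9. At the two-sided 95% limit of 9.1.2 the formula gives 71.6% left out and 68.3% with two failures.

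**Could a verdict turn?** For 8/24 v 2/24 the one-sided 95% Wald lower limit is 6.7 points. Two responses added per arm (10/26 v 4/26) bring it to 3.5, below the margin; two failures added (8/26 v 2/26) leave it at 5.9, still above. But 9.1.2 decides on the two-sided 95% limit, and there 8/24 v 2/24 gives 3.1 points and has already failed. At 9/24 v 2/24 the two-sided Wald limit is 6.9, falling to 3.4 at 11/26 v 4/26. Section 9.1.2 calls for an exact interval, however. An exact unconditional test of 9/24 v 2/24 at the 5-point margin gives p = 0.025 with the score statistic (0.0247, just under the one-sided 0.025 matching that limit) and 0.062 with the raw difference. Whether that result passes at all depends on the exact method.

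**The passages together.**

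1. Treatment is a single dose. Section 5.3.2, directly before 5.3.3, ties use of the data to drug administration, and 9.7.1 applies the same test. Read this way, the three sections agree.
2. The heading of 4.2.4.2 also covers Visits 2 and 3, so it labels a block of visits and does not define the start of treatment.
3. To count a Day 0 scan of an undosed woman as a response, an analyst must set aside 9.7.1 (she is not in the set), 7.2 (efficacy is judged at Visit 3) and 5.3.2 (use is limited to dosed women and to data from before withdrawal).

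**The case for a change.** The strongest reply is that this is more than detail left to the SAP: the Protocol twice names 9.5 as the place where the rule stands, and it is not there. That is correct. So is the point that, if therapy means dosing, 5.3.3 never says whether a woman randomised but not dosed is replaced.

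The case is firmer for dosed women withdrawn before discharge. They belong to the main set without any disputed reading. Section 4.2.4.4 orders an MRI that day, described as matching Visit 3 in content, and the endpoint wording names no day. Section 5.3.2 allows efficacy use only where possible and only of data from before withdrawal, and whether a scan on the day of withdrawal qualifies is not spelled out.

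These gaps stand, but they do not lead to a wrong analysis. Section 7.2 fixes the efficacy assessment at Visit 3, so an early scan is not the primary measurement and the woman's Visit 3 value is missing. How a missing value counts is ordinary SAP content, and 9.1 refers the complete analysis there. Counting such women as non-responders rather than leaving them out costs about 2.6 points of power at two per arm (81.2% to 78.6%), a modest choice either way. On replacement, the 26 randomised per arm already allow for two losses, and undosed women can be among them.

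**Conclusion.** No change to the plan follows. The reference to 9.5 is a clerical slip and the start of therapy is an undefined phrase; 5.3.2 and 9.7.1 supply the sensible meaning of both. Women withdrawn before dosing stay outside the main set. That is sound, because the decision to withdraw precedes exposure and is made under blinding, and it costs no stated power: 81.2% with 24 completers per arm.

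The less strained alternative, two failures per arm, would cost 2.6 points. The fall to 72.0% (75.1% by enumeration) is an upper bound. It assumes that both allowed losses in every arm occur before dosing, that all these women are scanned the same day and that every scan is scored as a response. The Protocol supports none of these assumptions.

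The conclusion rests on therapy meaning the dose, on blinding holding during surgery, on a 10% placebo rate and on no more than two such women per arm. With the 5% placebo rate printed in 9.2, power is 93.5% with these women left out and 91.8% with two failures per arm, so the effect is again small.

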5.3.4 Follow-up of female patients early terminated the study

Follow-up of female patients withdrawn from the study is not planned intentionally. See also section 4.2.4.4.

If a female patient was withdrawn from the study due to the reason of AR/SAR, she is followed up due to resolution of the AR/SAR or until the Investigator considers it to be “chronic” or “stable”. The follow up of female patients of the study withdrawn from the study and, in the meantime, having ARs or having other parameters of safety, which could cause therapy termination, is described in section 8.4.

6 Treatment of the study subjects

6.1 Dosage regimen of the test drug and the placebo

See section 4.4.4.

6.2 Previous and concomitant therapy

Previous therapy is intake of the drugs or non-drug therapy by a female patient *before the moment of inclusion into the study* (an information on the drugs received by female patient within 30 days before Visit 0 is collected).

Concomitant therapy is intake of the drugs or non-drug therapy by a female patient *at the moment of her inclusion into the study and in the period of participation in the study.*

Information on *previous therapy* will be collected and evaluated by Medical Investigator based on data of patient record/medical history and patient's questionnaire (collection of medical history) during selection of candidates for participation in the study and during screening period (Visit 0).

Information on *concomitant therapy* will be collected and evaluated by Medical Investigator based on data of patient record/medical history and patient's questionnaire of the study during the following periods:

- Administration of the test drug or the placebo (Visit 1);
- Follow-up visit (Visits 2-3).

Data on the drugs used for previous and concomitant therapy, dose, route and frequency of administration, dates of beginning and completion of the therapy, should be entered into primary documentation and into the CRF. Information on the test drug/placebo will be entered into a separate/specified for this section of the CRF.

6.2.1 Permissible previous and concomitant therapy

Any previous therapy, except for described in section **Ошибка! Источник ссылки не найден.**, is acceptable.

Female patients also may receive any drugs administered by a doctor and required for treatment of concomitant diseases/contraception, except for the drugs that may interfere with interpretation of new data obtained during the study (see section **Ошибка! Источник ссылки не найден.**). Decision on administration of the concomitant therapy drugs will be made by the Medical Investigator at his/her discretion and in case justified necessity of such an administration. Continuation of therapy with drugs not included into the list of forbidden therapy should be agreed before inclusion of patient into the study.

6.2.2 Forbidden previous and concomitant therapy

- During the surgery, it is forbidden to use any drugs intraperitoneally, except for normal saline or 0.02% chlorhexidine bigluconate as well as the test drug and the respective placebo before suture of surgical wound.
- Systemic glucocorticosteroids, cytostatics and other immunosuppressors.
- Anticoagulants, antiaggregants (except for acetylsalicylic acid at the dose of less than 325 mg/day).
- Oral contraceptives (combined drugs, containing estrogen component and progestogen, or progestogen only), used for at least 4 weeks/1 menstrual cycle before the first use and 4 weeks/1 menstrual cycle after the last use of the drugs compared.
- Injectable progestogen.
- Implants with progestogen.
- Vaginal ring containing estrogen and progestogen components.
- Transdermal system containing estrogen and progestogen components.

- Copper-containing intrauterine system.
- Levonorgestrel-releasing intrauterine system.

If during the study, it becomes necessary or it is established that the drugs or therapy methods specified in the present section are used, a female patient should be withdrawn from the study.

Use of forbidden or not specified by the protocol drugs and therapy methods

In case of single and/or irregular administration of the drugs specified in the present section, decision on inclusion of patient into the study is made by the Medical Investigator.

If during the study, it becomes necessary or it is established that the drugs or therapy methods specified in the present section are used, a female patient should be withdrawn from the study.

6.3 Methods of control for compliance with the procedures by the study subjects

6.3.1 Measures to provide compliance

In the present clinical study, the test drug and its respective placebo will be administered into cavity of the pelvis at the final stage of the surgery by the Medical Investigator once at Visit 1. Due to this, control of patient compliance with treatment is not required.

In order to provide compliance with the visit schedule, a coordinator of the clinical site preliminarily, before the scheduled outpatient visit, reminds the study subject on date and time of visit (phone call, fax, e-mail, etc.). If it is impossible to contact with the study subject, a phone call is made to a relative or connected person of the study subject. Attempts to contact with the study subject, her relative or connected person are made thrice.

Regardless of contact type, the Investigator receives a confirmation on received reminder from the study subject, on which a record is made in the Log of phone calls.

If the study subject can not visit the study site at the next scheduled visit, a possible postpone of visit is discussed considering acceptable deviations.

6.3.2 Evaluation of compliance

Not applicable. The drug is administered once, intraperitoneally by the staff of the clinical site.

7 Efficacy evaluation

7.1 List of efficacy parameters

Primary endpoint: achieving clinical efficacy determined as:

- Frequency of reducing number of adhesions after repeated MRI by 3 or more (in female patients with 10 and less adhesions at the baseline) or by 30% and more (in patients with >10 adhesions at the baseline)) in comparison to baseline MRI data

Secondary efficacy endpoints:

1. Change in thickness of pelvic adhesions by repeated MRI in comparison to baseline MRI data
2. Frequency of limited displaceability of pelvic organs in post-surgical period (based on results of transvaginal ultrasound investigation) on Day 30±4 after surgery
3. Frequency of hyperechoic linear lesions in post-surgical period based on results of transvaginal ultrasound investigation
4. Change in frequency of detecting limited displaceability in comparison to baseline (absolute change and in % of baseline value)
5. Change in frequency of detecting hyperechoic linear lesions in comparison to baseline (4 and less) based on repeated transvaginal ultrasound investigation
6. Frequency of detecting complete absence of USI – signs of adhesion process in the pelvis in post-surgical period (defined as absence of limited displaceability of pelvic organs and absence of hyperechoic linear lesions)

7.2 Methods and terms of evaluation, recording and analysis of efficacy parameters

Evaluation of efficacy of the study drugs Seroguard, solution 0.41 g/L (JSC Pharmasintez, Russia) and the Placebo will be performed for all the study subjects at Visit 3 based on considering parameters specified in section 8.1

8 Evaluation of safety

8.1 List of safety parameters

- Vital signs (body temperature, BP, HR, RR)
- Laboratory investigations:
 - Blood chemistry – total protein, glucose, ALT, AST, total bilirubin, alkaline phosphatase, amylase, creatinine
 - Complete blood count – RBC, WBC, platelet count, hemoglobin, hematocrit, WBC differential, ESR
 - Coagulogram – coagulation time, international normalized ratio (INR), thrombin time, activated partial thromboplastin time (APTT)
 - Urinalysis – color, transparency, pH, specific gravity, protein, glucose, WBC, RBC, bacteria, casts, salts
- ECG data – heart rate [HR], PR, QRS, QT intervals and calculated QTc interval

- USI data
- Incidence of adverse reactions
- Incidence of serious adverse reactions
- Incidence of unexpected adverse reactions
- Incidence of adverse and serious adverse reactions caused treatment discontinuation/withdrawal from the study

8.2 Methods and terms of evaluation, recording and analysis of safety parameters

Evaluation of safety of the study drugs Seroguard, solution 0.41 g/L (JSC Pharmasyntez, Russia) and the Placebo will be performed for all the study subjects at Visits 1-3, based on account of parameter, specified in section 8.1. Detection of adverse reactions (ARs) happens from the moment of signing informed consent to visit 3 inclusive. In addition, each study subject will be provided a phone number of the Investigator for contact in case of any problems with health. Clinical symptoms that will be developed after signing informed consent, but before use of the test drug or the placebo will be recorded as concomitant disease.

If the Investigator finds/receives information on AR, an unscheduled visit at the study site will be appointed in the nearest time (if required). At the moment of receiving information on AR, after analysis of AR and evaluation of risk for the study subject, the Investigator comes to a decision on delivery of required medical care. At the unscheduled visit, the Investigator makes decision on possibility of further participation of female patient in the study.

In case of indications, by the decision of the Medical Investigator or the physician, additional clinical and/or laboratory-instrumental investigations may be performed at unscheduled visits (see section 4.2.4.5).

The Investigator is responsible for notification of the Sponsor on any event considered as unusual, even if this event may be considered as unexpected benefit for the study subject.

Adverse reactions

AR means “any unintended and unfavorable reaction of the body which may be related to the drug administration” (Federal Law dated 12.04.2010 No 61-Φ3 “On drug circulation”).

AR severity grades

AR severity grade will be established as per the below classification:

- **Grade 1: mild.** Asymptomatic (detected at physical or laboratory-instrumental investigation) or with minimally pronounced symptoms, easily tolerable by a subject, causing minimum discomfort and not interfering with normal activity, not requiring special treatment;

- **Grade 2: moderate.** Causing discomfort, limiting normal activity; requiring medical aid without invasive interventions (for example, applying a dressing);
- **Grade 3: severe.** Making normal activity impossible; disabling; requiring invasive intervention; requiring hospitalization; life-threatening; death.

Causal relation of AR to administration of the study drugs

Causal relation of AR to administration of the study drugs will be evaluated based on criteria of the World Health Organization (WHO):

- **Definite.** Clinical manifestations of AR, including laboratory abnormalities, observed during administration of the drugs, which may not be explained by presence of current diseases and influence of other factors and chemical compounds. Side reaction manifestation regress after the drug withdrawal and develop after re-administration.
- **Probable.** Clinical manifestations of AR, including laboratory abnormalities, related to time of the drug administration, which are unlikely related to concomitant diseases or other factors and which regress after the drug withdrawal. Response reaction to re-administration is unknown.
- **Possible.** Clinical manifestations of AR, including laboratory abnormalities, related to time of the drug administration, which may be explained by presence of concomitant diseases or administration of the other drugs and chemical compounds. Information on reaction to withdrawal of the drug is unclear.
- **Unlikely.** Clinical manifestations of AR, including laboratory abnormalities, which develop with no clear temporary relation to the drug administration; there are other factors (drugs, diseases, chemical substances), that may be a reason of their development.
- **Conditional.** Clinical manifestations of AR, including laboratory abnormalities, related to “side reactions”, that require obtaining additional data (for accurate estimate) or these obtained data are analyzed at present.
- **Unclassified.** Reports on suspected side reaction may not be evaluated, because the information is not sufficient or it is contradictory.

Serious adverse reaction or unexpected adverse reaction

Serious AR (SAR) is an adverse reaction of the body related to the administration of the drug that led to death, congenital anomaly or birth defects or life-threatening, requiring hospitalization or incapacitating and (or) disabling (Federal Law dated 12.04.2010 No 61-Φ3 “On drug circulation”).

In case of SAR development in the study subject, administration of the study drug is discontinued, the Medical Investigator completes the respective section of the CRF of the study subject and SAR Report Form.

If SAR develops, the Investigator (if required) must take actions to provide respective qualified medical assistance to the study subject, including performance of clinical and/or laboratory-instrumental investigations.

In this case, follow up of the study subject should be continued before resolution/stabilization of the SAR observed.

Unexpected adverse reaction

Unexpected AR (UAR) is an adverse reaction of the body which is related to administration of the drug at the doses recommended in the protocol of the clinical study, Investigator' brochure, or to administration of the drug at the doses recommended in the package insert on its use for prevention, diagnostics, treatment of diseases or medical rehabilitation of patient, and nature, severity and outcome of which do not correspond to information on the drug, contained in the protocol of the clinical study, Investigator's brochure or in package insert of the drug (Federal Law dated 12.04.2010 No 61-Φ3 "On drug circulation")

Pregnancy

See section 8.3.

Deviations in values of laboratory and instrumental investigation parameters

Deviations from the normal (values accepted in the respective clinical site) results of laboratory or instrumental investigations are considered as clinically significant and, respectively, as ARs, if they are:

- confirmed in repeated investigation;
- accompanied by clinical manifestations or symptoms;
- accompanied by withdrawal of a female patient from the study;
- confirm development of disease/manifestation of toxic properties of the study drug;
- require appointing unscheduled visits, additional diagnostic procedures and/or therapeutic measures;

AR outcome

AR outcome is indicated to the moment of time when it is documented as per the following categories:

- recovered/resolved (no signs of AR completely);
- recovering/resolving (regress of sign/symptom of AR, incomplete disappearance);
- recovered/resolved with sequelae;
- not recovered/not resolved (AR existing at the moment of documentation or at the moment of death of the study subject due to any reason or due to development of another AR);
- lethal outcome (death due to developed AR);
- no data (for example, if the study subject did not come for final examination or follow-up visit and cannot be contacted).

8.3 Requirements to reports, procedures for recording and reporting adverse reactions and intercurrent diseases

Adverse event recording

If any AR develops, the Investigator should complete the respective sections of the CRF of the study subject, evaluate feasibility of continuing the study by female patient (exclude the study subject or continue participation of female patient in the study). ARs will be recorded from the moment of the study drug administration and to completion of the final visit (Visit 3).

For each AR, the following information should be recorded in the primary medical documentation:

- AR nature as per the ICD-10 terminology system (International Classification of Diseases 10th revision);
- severity grade (mild/ moderate/ severe AR);
- causal relation to administration of the test drug/reference drug (definite/ probable/ possible/ unlikely/ conditional/ unclassified);
- duration (start date and time / stop date and time);
- outcome (resolved/ resolving/ resolved with sequelae/ not resolved / lethal outcome/ no data);
- is AR serious.

Report on serious adverse reaction to the Sponsor

In case of SAR, it is necessary to record the fact of SAR development in the primary documentation and complete respective pages of the CRF of the study subject.

Information on SAR should be sent to the pharmacovigilance officer of JSC Pharmasyntez, [name] within 24 hours:

- [contact];
- [contact];
- E-mail: [contact].

A special form of serious adverse reaction is completed in this case (see section 17.1), original of which is sent to JSC Pharmasyntez to the following address: [name].

Notification form should be sent, even if the Investigator has incomplete volume of information on SAR. However, after the primary report on SAR, the Investigator should always inform on evaluation of degree of SAR relation to the administration of the study drug (see section 8.2). The Investigator should receive confirmation that the information is delivered.

If provided by the current requirements, the Sponsor will send respective notifications on AR to appropriate healthcare authorities.

Pregnancy during the study

Before the study beginning, female patients are instructed on effective methods of contraception used throughout the study. All the study subjects pass pregnancy test at Visit 0, 3 or at Withdrawal Visit (see section 4.2.3.5), they are also instructed on required obligatory notification of the Investigator at any time when pregnancy is suspected. In this case, during the next/unscheduled visit, a pregnancy test is repeated (using test-strip, see section 4.2.3.5) and, if required, a concentration of beta-chorionic gonadotropin in blood is determined, and examination by gynecologist is performed. If fact of pregnancy is confirmed, female patient discontinues her participation in the study (see section **Ошибка! Источник ссылки не найден.**).

